Great strides have been made in AIS treatment over the last decade; however, lack of a quantitative, bedside/field-based diagnostic severely which is suitable for hospital/prehospital use limits access to treatment. We were able to show positive results in a feasibility study (EXPEDITE) of 66 subjects (33 LVOs) for LVO diagnosis in the ER setting using a newly developed TCD-derived digital biomarker termed Velocity Curvature Index (VCI) [15,16]. The VCI biomarker which leverages a machine learning platform which leverages data produced by the NovaGuide System (NovaGuide Robotic System – K180455, NovaSignal Corp., Los Angeles, CA USA). The NovaGuide, a combination of the Lucid M1 System (510k K160442) and the NovaBot accessory, utilized in both phases of the proposed research plan, is capable of TCD signal acquisition in the hospital setting without need of a trained TCD technician for operation or interpretation. Phase I will establish baseline performance characteristics of the hemodynamic biomarker (VCI) and define the study characteristics and context of use for FDA submission. Phase II will provide a comprehensive, multi-site data set for full analytic validation of the biomarker, with the goal of regulatory submission for an expanded indication. The availability of this biomarker will have several potential applications including, monitoring post-intervention patients and supplement triage and transfer protocols for patients suspected of LVOs, which will result in potentially faster and more widespread access to intervention, affording vastly improved outcomes for thousands of potential patients each year. The analogy to the use of EKG for myocardial infarction (MI) which supplements clinical evaluation and more invasive imaging.

TCD ultrasonography is a safe, non-invasive, and reproducible technique that allows the assessment of cerebral blood flow velocity (CBFV) in the large conducting arteries of the head and neck. TCD data collection relies on the level of experience of a TCD technologist to acquire an accurate and high-quality signal from the intracranial vessel(s) of interest, thus per user, the data quality is variable. NovaSignal has developed the NovaGuide System to assist in the TCD data collection such that consistent high-quality data may be obtained independent of the experience of the user.

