4.2.2 Phase 2 Study Endpoints

Phase 2 Primary Endpoint:

- Area Under the Curve (AUC), Sensitivity, and Specificity of VCI when compared against standard of care CTA imaging for large vessel occlusion assessment.

Phase 2 Secondary Technical Efficacy Endpoint:

- Area Under the Curve (AUC), Sensitivity, and Specificity of a novel machine learning (ML) algorithm when compared against standard of care CTA imaging for large vessel occlusion assessment.

- VCI and experimental ML algorithm compared to prehospital/neurological clinical scales for alternative diagnostic criteria.

Phase 2 Primary Safety Endpoint:

- Incidence of device-related serious adverse events
- Last Known Normal (LKN) to First Hospital Arrival (Initial Door-In) time
- Door to Initial CT imaging (non-contrast) time
- Door to IV-tPA time
- Door to Initial CTA Acquisition time
- Door to Groin Puncture time
- CTA Acquisition to Groin Puncture time

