11 STATISTICAL ANALYSIS

11.1 Phase 1 Statistical Analysis:

Primary Endpoint Analysis: Demonstration of VCI diagnostic performance at or exceeding 85% ROC-AUC (targeting SEN greater than 90%) to standard of care imaging.

Biomarker Validation and Analysis: VCI will be computed for each subject according to the procedure outlined in section 3.5, and group differences will be assessed using appropriate statistical methods. ROC-AUC will be computed detailing separability between groups for comparison to standard of care imaging (CTA) and prehospital/neurological clinical scales, along with SEN, SPE, and accuracy at various levels of diagnostic threshold, including that corresponding to Youden's maximal J-statistic.

Sample size calculation: From the results of our feasibility study, we estimate that expected effect size between VCI distributions for LVO (cohort A) and IHC groups (cohort B) will be large (Cohen's $D > 1.25$), such that only a small number of subjects in each group ($N = 11$) will be sufficient to detect significant differences (alpha of 0.05) with standard statistical power of 80%. However, in Phase 1 we seek to demonstrate the stronger aim of biomarker diagnostic performance in excess of 85% ROC-AUC. Assuming this target AUC is met, then sample size determines the confidence bounds on that estimate. In Phase 1 we require a sample of sufficient size to power confidence in the superiority of VCI diagnostic performance relative to current clinical prehospital stroke assessment scales. As existing preclinical scales top out at 78% AUC, this can be accomplished with a sample of roughly 50 subjects in each patient group, which gives a one-tailed 95% confidence bound on the target 85% AUC of less than 7%. The specification of 54 subjects per group is a target number intended to guarantee acquisition of a sufficient sample assuming at least 90% of target enrollment.

Initial safety endpoint analysis: Throughout the study we will collect adverse events, which will be used to determine the safety of the device within the acute stroke environment. In our EXPEDITE study which is also run in the ER for stroke assessment, the device has been designated minimal risk by the IRB and we have not had any serious adverse events in over 80 subjects. We will continue to closely monitor this metric.

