11.2 Phase 2 Statistical Analysis

Primary Endpoint Analysis: Demonstration of VCI biomarker performance at or exceeding 90% ROC-AUC (targeting SEN & SPE greater than 90%) to standard of care imaging across multiple centers.

Here, we will determine the final biomarker performance using the dataset collected and reviewed by the core lab. Similar analyses will be run on the VCI biomarker distributions for the Phase 2 subject group as was done in Phase 1. Additionally, subgroup analyses comparing biomarker results across research sites, and age groups, will be conducted to determine if any age or NovaGuide inter-operator variability effects are present in the data (two-way ANOVA with post-hoc comparisons).

Sample size calculation: In Phase 2, we seek to demonstrate stricter confidence bounds on biomarker diagnostic performance in excess of 90% ROC-AUC. Assuming the biomarker is observed to meet that performance threshold, then a sample of approximately 150 LVO subjects in each patient group is required to attain a one-tailed 95% confidence bound on the observed AUC of 3%. That is, the target AUC and sample size would afford 95% confidence that the underlying general population AUC is greater than 87%. Moreover, across five sites, this results in approximately 30 LVO subjects per site, affording sufficient power for detection of moderate potential inter-site effects in the range of Cohen’s $D \geq 0.75$.

Calculate study and site specific stroke workflow times: Stroke workflow parameters and times are well characterized in literature, including “Get with the Guidelines, Stroke” published by the American Heart Association, Inc. and will be utilized as a historical control comparator for data collected in Phase 2. We will use these published stroke guidelines which have mean times for the stroke workflow parameters to show that we are non-inferior to these when using the NovaGuide device. Additionally, the data will be compared to the corresponding randomized group (Cohort C and D)

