11.5 Data Analysis

Evaluation of correlation between diagnostic imaging standard of care and VCI biomarker by an independent core laboratory masked to local radiology determination. Success criteria will include clinical validation of VCI biomarker for LVO detection threshold performance at or exceeding 90% ROC-AUC (targeting SEN & SPE greater than 90%) to standard of care imaging.

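### Phase 2 sensitivity and specificity are part of the primary endpoint, but no VCI cut-off is fixed for them, and the only threshold rule in the plan would pick it from the same subjects

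*Combined protocol and SAP*

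**What the plan says.** - Section 4.2.2 gives the Phase 2 primary endpoint as "Area Under the Curve (AUC), Sensitivity, and Specificity of VCI when compared against standard of care CTA imaging for large vessel occlusion assessment". No cut-off is attached.
- Section 11.2 sets the Phase 2 aim as "performance at or exceeding 90% ROC-AUC (targeting SEN & SPE greater than 90%) to standard of care imaging across multiple centers". Section 11.5 repeats it at study level: "Success criteria will include clinical validation of VCI biomarker for LVO detection threshold performance at or exceeding 90% ROC-AUC". A threshold is mentioned there, but none is named.
- Section 11.1 has the only threshold rule, written for Phase 1: "SEN, SPE, and accuracy at various levels of diagnostic threshold, including that corresponding to" the maximum of Youden's J.
- Section 11.2 then says "Similar analyses will be run on the VCI biomarker distributions for the Phase 2 subject group as was done in Phase 1", and describes the data to be used as follows: "we will determine the final biomarker performance using the dataset collected and reviewed by the core lab".
- Section 2 gives Phase 2 its role: "Phase II will provide a comprehensive, multi-site data set for full analytic validation of the biomarker".
- Section 3.5 explains how VCI is computed but gives no decision value. No section locks a cut-off after Phase 1, sets aside a hold-out sample or plans an optimism correction.

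**The concern.** AUC summarises all cut-offs at once. Sensitivity and specificity do not exist until one cut-off is named, so part of the Phase 2 primary endpoint is undefined. If Section 11.2 is followed by repeating the Phase 1 analysis, the cut-off is the one that looks best in the Phase 2 sample, and the same sample then measures its performance. The estimates are biased upward, and ordinary confidence intervals ignore the search. Reporting at several thresholds adds a second freedom, because the one that is highlighted can be chosen after the results are seen.

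Phase 2 is labelled pivotal and is meant to validate the biomarker for a regulatory submission. A triage tool is used at one cut-off, so its error rates at that cut-off are what a reader will take from the trial. With the cut-off left open, a result just above 90% could reflect the choice of threshold.

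**Working it through.** **1. The plan's own figure.** Section 11.2 says about 150 per group give a one-tailed 95% bound of 3 points on an AUC of 90%. The Hanley-McNeil formula for n per group is SE² = [A(1−A) + (n−1)(a−A²) + (n−1)(b−A²)]/n², with a = A/(2−A) and b = 2A²/(1+A). For A = 0.90, a = 0.8182 and b = 0.8526. For n = 150, SE = 0.01845, 1.645 × SE = 0.0304, and the lower bound is 0.870. At the enrolment target of 156 the half-width is 0.0298. The plan's figure reproduces and involves no cut-off.

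**2. Inputs for the check.** From the documents: 156 per group in Phase 2, 54 per group in Phase 1, and targets above 90%. Assumed, because the documents give no VCI distribution: non-LVO scores N(0,1) and LVO scores N(d,1), with d = √2·Φ⁻¹(AUC). The best cut-off then gives SEN = SPE = Φ(d/2):

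- AUC 0.90: d = 1.812, best SEN = SPE = 81.8%
- AUC 0.95: d = 2.326, best 87.8%
- AUC 0.965: d = 2.563, best 90.0%

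More than 90% of 156 means at least 141, since 140/156 = 89.7% and 141/156 = 90.4%.

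**3. Fixed cut-off at the true optimum.** P(both > 90%) = P(Bin(156, p) ≥ 141)². For p = 0.900 this is 0.504² = 0.254. For p = 0.878 it is 0.196² = 0.038.

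**4. Cut-off chosen in the Phase 2 sample.** Monte Carlo, 8,000 runs per scenario, 156 per group. Optimism is apparent SEN + SPE at the in-sample Youden cut-off minus the true SEN + SPE at that same cut-off.

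| True AUC (best SEN = SPE) | Optimism in SEN + SPE | Both > 90%: fixed | Both > 90%: Youden | Both > 90%: any cut-off |
|---|---|---|---|---|
| 0.90 (81.8%) | 3.3 points | about 0 | 0 in 8,000 | 0 in 8,000 |
| 0.95 (87.8%) | 2.8 points | 3.8% | 6.4% | 11.4% |
| 0.965 (90.0%) | 2.6 points | 25% | 31% | 51% |

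Halving the optimism gives about 1.3 to 1.7 points on each measure. Repeat runs moved the Youden and any-cut-off percentages by about one point. The last column is a worst case: any cut-off that meets both targets is accepted.

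**5. Intervals.** In 6,000 runs at each AUC, the lower limit of an exact 95% interval lay above the true value in 4.9 to 5.9% of runs at the Youden cut-off. At a fixed cut-off this was 1.2 to 2.2%, against a nominal maximum of 2.5%.

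**6. Cost of locking a cut-off from Phase 1.** An independent sample sets the cut-off, which is then applied to 156 per group. The pass chance is for a marker with true best 90%/90%.

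| Cut-off rule | Phase 1 n per group | True SEN + SPE lost against the optimum | Both > 90% |
|---|---|---|---|
| Raw Youden | 54 | 1.4 to 1.8 points (over the AUCs studied) | 11% |
| Midpoint of group means | 54 | about 0.2 points | 19% |

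With 87 per group (54 plus 33 from the feasibility study) the pass chances are 12.5% and 21%. Section 2 reports 66 feasibility subjects with 33 LVOs; that the other 33 are comparable non-LVO subjects is an assumption.

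**The case against.** **AUC is the firm criterion.** Sensitivity and specificity above 90% are worded as targets, with no null value, alpha or pass/fail test, and the sample size rests on AUC alone. This is correct and limits the severity. They are still named in the primary endpoint, so they need a definition.

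**The in-sample search is inferred.** The Section 11.2 wording does not exclude applying a Phase 1 cut-off, and Section 2 has Phase 1 set baseline performance and context of use. That is true, but no carry-forward is written. Under either reading the cut-off is missing from the plan.

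**The effect is small.** At AUC 0.90, the value used for planning, no route reaches 90%/90%. The larger pass probabilities need an AUC of 0.965, which the documents do not mention, and the any-cut-off column is an extreme. The optimism is also small beside sampling error: 141/156 has an exact 95% interval of 84.6% to 94.5%. All of this stands. Selection affects the 90% target only for a marker already close to it, though the optimism is present at every AUC examined.

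**Intervals for sensitivity and specificity are not in the plan.** The documents describe confidence bounds only for AUC. The coverage result therefore shows what would follow if ordinary intervals were added; it is not a fault in a planned interval.

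**Blinding helps.** Section 5.3 blinds the clinical team to VCI and the sponsor to the comparison of VCI with CTA. This limits deliberate choice of a threshold, but it does not remove the optimism of a Youden point computed once the two are joined.

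**Conclusion.** The concern holds and should be fixed. The plan names no cut-off for two of the three parts of its Phase 2 primary endpoint, and the only rule it offers would select the cut-off in the validation sample without correction. The resulting bias is modest: about 1.3 to 1.7 points each on sensitivity and specificity at 156 per group. For a marker truly at 90%/90%, the chance of both exceeding 90% rises from 25% to about 31% with Youden, and to about 51% with free choice.

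These sizes rest on an equal-variance binormal model and on assumed AUCs of 0.90 to 0.965. That the cut-off is unspecified rests on the text alone. The AUC criterion and its sample size are not affected.

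**What to change.** In Section 11.2, state that one VCI cut-off is derived from Phase 1 and feasibility data and recorded in a dated document before any Phase 2 VCI value is compared with core-lab CTA. State the derivation rule. A smoothed or model-based rule, such as the midpoint of the group means, is steadier than the raw Youden point. Report Phase 2 sensitivity and specificity together at that cut-off, in Phase 2 subjects only, with exact confidence intervals. Label the Phase 2 Youden point and all other Phase 2 thresholds exploratory. If the sponsor prefers to keep a Phase 2 Youden cut-off as the main result, the fallback is a pre-specified bootstrap or cross-validated optimism correction.

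The machine learning algorithm has the same gap in its secondary endpoint: sensitivity and specificity are listed without a cut-off, and no training and test data are separated. Lock the model and its cut-off at the same time.

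The cost is one paragraph and a lock document, with no extra subjects. Phase 2 sensitivity and specificity will look slightly lower, and a cut-off set from 54 per group can miss the optimum. In the calculation above, the pass chance at true 90%/90% is 19% with the midpoint rule and 11% with raw Youden, against 25% at the ideal cut-off.

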Study Sponsor: NovaSignal Corp. [name] National Institute of Health (NIH)	Protocol No.: NA-01STR-03 Regulatory Class: II Study Device(s): NovaGuide and/or Lucid TCD System Development Phase: Phase 1: Feasibility; Phase 2: Pivotal
3. Subjects who underwent partial or full craniotomy 4. Additional intracranial pathologies present (tumor, hydrocephalus, etc.) 5. Anticipated insufficient time to acquire a complete initial TCD scan as described by the protocol 6. Subjects who have a physical limitation preventing placement of the system.	
Cohort B Non-LVO	
Inclusion Criteria	
1. Subject aged 18 years and older 2. Non-large vessel occlusion confirmed by computed tomography angiography (CTA) 3. Subject or Legally Authorized Representative has the ability to provide informed consent and comply with the protocol.	
Exclusion Criteria	
1. CTA findings including: a. Occlusions in the common carotid artery, internal carotid artery, anterior carotid artery, middle cerebral artery (M1 and M2 segments), anterior communicating artery, basilar artery, posterior communicating artery and vertebral arteries. 2. Head CT findings consistent with acute primary intracranial hemorrhage (SAH, ICH, etc.) 3. Hemodynamically unstable patients requiring pharmacological support for hypertension 4. Subjects who underwent partial or full craniotomy 5. Anticipated insufficient time to acquire a complete set of scans as described by the protocol 6. Subjects who have a physical limitation preventing placement of the system.	
Phase 2 Study Design	
Phase 2 will include up to 312 subjects (156 cohort A and 156 in cohort B) presenting with stroke like symptoms for which diagnostic imaging has been ordered. Primary and secondary endpoints will be calculated after completion of Phase 2.	

Protocol Synopsis:	
Study Sponsor: NovaSignal Corp. [name] National Institute of Health (NIH)	Protocol No.: NA-01STR-03
	Regulatory Class: II
	Study Device(s): NovaGuide and/or Lucid TCD System
	Development Phase: Phase 1: Feasibility; Phase 2: Pivotal
Imaging Core Lab Analysis: All imaging data will be sent to a core laboratory which will provide independent quantitative and qualitative assessment of all study data. They will be blinded to the study and radiology report data and provide independent review.	

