4.9 Randomization

Randomization will occur once subject has satisfied all inclusion/exclusion criteria and informed consent has been obtained. Subjects will be randomly assigned in equal number (1:1) to one of two procedure arms within each cohort: 1) TCD Exam or 2) No TCD Exam. The number of procedures and controls will be balanced within investigational sites, by baseline NIHSS severity (≤ 17 versus >17), age (<70 years versus ≥ 70 years at the time of randomization) occlusion location (M1 versus all other), and time of day of initial CT scan (0900-1700 and 1701-0859). Subject allocation to procedure will be accomplished by using an interactive web response (IWRS) or interactive voice response system (IVRS).

At the time of randomization, the site will access IVRS/IWRS and enter subject's screening NIHSS, age, occlusion location, and time of CT scan. Based on the information provided, the system will automatically generate the assigned treatment. If the site is unable to access website for randomization, an interactive voice response randomization is also available by phone.

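### Section 11.2 looks for an age effect on VCI by comparing undefined age groups; a continuous age term would detect small and moderate effects better, and the role of LVO status needs stating

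*Combined protocol and SAP*

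**What the plan says.** Section 11.2 (Phase 2 Statistical Analysis) plans "subgroup analyses comparing biomarker results across research sites, and age groups, will be conducted to determine if any age or NovaGuide inter-operator variability effects" on VCI. The method named is "two-way ANOVA with post-hoc comparisons". Site and age group are the only factors mentioned. The section does not define the age groups, state the analysis set, mention LVO status or an interaction, or give an age effect size or power.

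The only age cut in the documents is in section 4.9 (Randomization), where "age (<70 years versus ≥ 70 years at the time of randomization" is one of the factors balanced between the TCD and No TCD arms within each cohort. Under the same section the site enters each subject's age at randomization, so the age analysis needs no new data item.

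On size, the synopsis says "Phase 2 will include up to 312 subjects (156 cohort A and 156 in cohort B". The one power remark close to the ANOVA concerns sites, not age: "across five sites, this results in approximately 30 LVO subjects per site, affording sufficient power for detection of moderate potential inter-site effects", for a Cohen's D of 0.75 or more.

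**The concern.** Comparing groups discards the age differences within each group. If VCI drifts steadily with age, a grouped comparison is less likely to show it than a slope fitted to age in years. This is the only planned check of whether VCI depends on age, in a phase meant to support an expanded indication.

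The second issue is the analysis set. The sentence before the ANOVA speaks of the Phase 2 subject group, which contains both cohorts. The power remark counts LVO subjects only. If the model pools both cohorts without LVO status, two things follow. The large LVO difference goes into the residual and hides an age effect. Any difference in mean age between LVO and non-LVO subjects can also appear as an age effect, because randomization balances age between arms within a cohort, not between cohorts.

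**Working it through.** **The plan's own figures.** They reproduce.
- Phase 1, D = 1.25, alpha 0.05, 80% power (section 11.1: "sufficient to detect significant differences (alpha of 0.05) with standard statistical power of 80"): n = 2(1.96 + 0.842)²/1.25² = 10.05, so 11 per group.
- Phase 2, AUC 0.90, 150 per group: the Hanley-McNeil standard error is 0.01845, and 1.645 × 0.01845 = 3.04%, against the stated 3%.
- Sites, D = 0.75: n = 2(1.96 + 0.842)²/0.75² = 27.9, so 28 per site. With 30 per site, power is 81% to 83%.

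There is no stated figure for age to reproduce.

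**Inputs for the age check.**
- From the documents: five sites, about 150 LVO subjects (about 300 in both cohorts), and D above 1.25 between cohorts (section 11.1: "expected effect size between VCI distributions for LVO (cohort A) and IHC groups (cohort B) will be large"). The Phase 2 AUC target of 0.90 implies D = √2 × Φ⁻¹(0.90) = 1.81 for two normal distributions of equal variance.
- Assumed: a linear age effect with within-cohort correlation r, normally distributed age with mean 70 and SD 13, a two-sided alpha of 0.05, and a cut at 70 borrowed from section 4.9.

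**Step 1: cutting age, LVO subjects only.** A median split keeps a fraction e = 2/π = 0.637 of the age information. The F-test noncentrality is
- continuous age: N r²/(1 − r²);
- cut age: N r² e/(1 − r² e).

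At N = 150 and r = 0.20 these are 150 × 0.04/0.96 = 6.25 and 150 × 0.0255/0.9745 = 3.92. Power, with residual degrees of freedom for five sites (and for the site-by-age interaction in the cut model), beside a simulation of the same setting:

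| r | Continuous, formula | Cut at 70, formula | Loss | Simulation, continuous vs cut |
|---|---|---|---|---|
| 0.10 | 23% | 16% | 7 | loss about 6 |
| 0.15 | 46% | 31% | 14 | 44% vs 28% |
| 0.20 | 70% | 50% | 20 | 69% vs 50% |
| 0.25 | 88% | 70% | 18 | 85% vs 68% |
| 0.30 | 97% | 85% | 12 | 96% vs 83% |

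Losses are taken before rounding. A separate simulation gave losses of 15, 20, 17 and 13 points at r = 0.15 to 0.30. By the formula the loss is about 5 points at r = 0.35 and nil at r = 0.50. Finer grouping did not help: four groups (cuts at 60, 70 and 80) gave 24%, 44%, 66% and 82% at r = 0.15 to 0.30.

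**Step 2: if pooled without LVO status.** Omitting LVO adds D²/4 to a within-cohort variance of 1. At D = 1.25 the residual variance is 1.39 (SD 1.18 times larger); at D = 1.81 it is 1.82 (SD 1.35 times larger). With N = 300 and r = 0.20:
- continuous age plus LVO term: noncentrality 300 × 0.04/0.96 = 12.5, power 94% (simulation about 93%);
- cut age, no LVO term, D = 1.25: 300 × 0.0255/(0.9745 + 0.3906) = 5.60, power 65% (simulation about 65%);
- cut age, no LVO term, D = 1.81: 300 × 0.0255/(0.9745 + 0.8212) = 4.25, power 54% (simulation about 52%).

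**Step 3: false positives if pooled without LVO status.** Suppose there is no age effect but mean age differs by 4 years between cohorts (72 and 68). The share aged 70 or over is Φ(2/13) = 0.561 in one cohort and 0.439 in the other. The two age groups then differ in LVO share by 0.122, hence in mean VCI by 0.122 D. With 150 per age group:
- D = 1.25: difference 0.153, standard error 1.18 × √(2/150) = 0.136, z = 1.12, so about 20% significant;
- D = 1.81: difference 0.222, standard error 0.156, z = 1.42, so about 30% significant.

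With an LVO term the rate is about 5%.

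**The case against.** The strongest reply is that section 11.2 never says the ANOVA pools the cohorts. The count of LVO subjects per site fits a within-LVO comparison, where no LVO term is needed and steps 2 and 3 do not apply. A reader might infer that the plan leaves LVO status out of a pooled model. That would be reading silence as a decision, and the documents do not support it. What stands is that the analysis set has to be stated.

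A reader might also infer that a non-significant result will be taken to mean VCI does not depend on age. No rule in the documents says so. What stands is that the stated aim is to determine whether an effect is present, and no estimate or interval is planned.

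The power losses rest on an age effect, age spread and cohort age gap that the documents do not give. At r = 0.15 to 0.30 age explains only about 2% to 9% of the variance in VCI (r² = 0.0225 to 0.09). Groups also have one merit: they assume no shape for the age effect.

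Finally, this is a subgroup check with no success criterion attached. All of that is fair and sets the weight of the point. It does not remove the advantage of continuous age, which holds under either analysis set when the effect is roughly linear.

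**Conclusion.** The point holds as a minor improvement to a secondary analysis. The plan names a grouped-age ANOVA where a continuous age term is available and more powerful for a roughly linear effect of small or moderate size.

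The loss from grouping alone, in about 150 LVO subjects, is about 6 points at an assumed r of 0.10 and about 13 to 20 points at 0.15 to 0.30. These figures describe assumed scenarios and are not a property of the plan.

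The larger pooled losses (about 52% to 65% power against about 93% at r = 0.20) and the 20% to 30% false positives are conditional. They need a pooled model with only site and age group as factors, and the false positives also need an assumed 4-year age gap between cohorts. The documents confirm neither condition. The Phase 2 AUC analysis and its success criterion are unaffected.

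**What to change.** In section 11.2, replace the site-by-age-group ANOVA with a linear model of VCI on LVO status, site and age in years. Add an age-by-LVO term, because an age main effect alone does not show whether the separation between LVO and non-LVO changes with age. Pre-state a curvature check, such as a quadratic or spline term. Fitting the site and age model within each cohort is an acceptable alternative; either way, state the analysis set.

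Report the age slope with its confidence interval, so that a non-significant result shows which effects remain possible. Keep the site comparisons. Define any age groups in advance and use them for descriptive summaries only.

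The cost is a few sentences in the plan, with no new data or subjects. The small downside is an assumed shape for the age effect, which the curvature check covers.

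### The Phase 2 site and age ANOVA does not name LVO status as a factor or state its analysis set, and comparing VCI level does not test whether LVO/non-LVO separation is consistent.

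*Combined protocol and SAP*

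**What the plan says.** Section 11.2 (Phase 2 Statistical Analysis) first says that "Similar analyses will be run on the VCI biomarker distributions for the Phase 2 subject group as was done in Phase 1". It then adds that "subgroup analyses comparing biomarker results across research sites, and age groups, will be conducted", the purpose being "to determine if any age or NovaGuide inter-operator variability effects are present in the data (two-way ANOVA with post-hoc comparisons". Site and age group are the only groupings named. The outcome, factor list, interaction terms, age cut, analysis set and post-hoc method are not given.

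The sample-size paragraph of the same section notes that "across five sites, this results in approximately 30 LVO subjects per site". It regards this as enough to detect differences between sites of D = 0.75 or more, and attaches no power figure.

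Two other statements give the expected size of the LVO effect on VCI. Section 11.1 expects that the difference between the cohorts "will be large (Cohen's $D > 1.25$), such that only a small number of subjects in each group ($N = 11$) will be sufficient". The Phase 2 primary aim in section 11.2 is "Demonstration of VCI biomarker performance at or exceeding 90% ROC-AUC".

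Section 4.4 plans 156 subjects in each cohort overall. Section 4.9 balances TCD against No TCD within cohort and site. Neither section fixes the share of LVO subjects at a site or the age distribution of a cohort.

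**The concern.** VCI is being developed because it differs strongly between LVO and non-LVO subjects. An ANOVA of VCI on site and age group that pools the cohorts without a term for LVO status has two weaknesses. The LVO difference is counted as noise, so real site or age effects are harder to see. And if sites or age groups differ in their proportion of LVO subjects, that difference in case mix shows up as a site or age effect.

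A third weakness does not depend on pooling. Performance across centres means that VCI separates LVO from non-LVO equally well everywhere. A comparison of mean VCI does not ask that question. At stake is the one planned analysis that would support a claim of consistency across centres and ages: it could flag a difference that is only case mix, miss a real one, or find nothing while diagnostic performance varies.

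**Working it through.** **Inputs.** D = 1.25 (section 11.1); target AUC 0.90, five sites, about 30 LVO subjects per site and D = 0.75 for site effects (section 11.2); 156 + 156 scanned subjects (section 4.4), so 312/5 ≈ 62 per site. Alpha 0.05 and 80% power are stated for Phase 1 only and are assumed here. Within-cohort SD is set to 1.

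**The plan's own figures.**
- Subjects per group for D = 1.25: 2(1.960 + 0.842)²/1.25² = 10.05, rounded up to 11. This matches section 11.1.
- Subjects per site for D = 0.75: 2(1.960 + 0.842)²/0.75² = 27.9, rounded up to 28 (29 with the t distribution). Power at 30 per site is Φ(0.75·√(30/2) − 1.960) = 0.83 (t-based 0.815).

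The inter-site claim therefore reproduces as an unadjusted comparison of two sites within LVO subjects.

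**Size of the LVO effect.** AUC 0.90 corresponds to D = √2·Φ⁻¹(0.90) = 1.81 if the two distributions are normal with equal variance (an assumption). At a 50:50 mix the LVO difference adds D²/4 to the variance.

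| | D = 1.25 | D = 1.81 |
|---|---|---|
| LVO share of variance, (D²/4)/(1 + D²/4) | 0.39/1.39 = 28% | 0.82/1.82 = 45% |
| SD inflation, √(1 + D²/4) | 1.18 | 1.35 |
| A true 0.75 acts like | 0.75/1.18 = 0.64 | 0.75/1.35 = 0.56 |

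**Power of the site F-test.** Take 5 sites × 62, an equal mix at every site, and one site shifted by 0.5. The mean shift is 0.1, so the squared deviations sum to 0.4² + 4 × 0.1² = 0.20 and the noncentrality is 62 × 0.20 = 12.4. With LVO in the model, power is about 0.81. With LVO omitted, simulation gives about 0.60 (D = 1.25) and 0.40 (D = 1.81). The loss exceeds what the SD inflation alone implies because, with the mix fixed equal at each site, the test becomes too conservative: its actual size is 0.01 and 0.002.

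**False positives with LVO omitted and no true effect** (simulated at nominal 0.05; the mixes are assumptions, since the documents give none).

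| Scenario | D = 1.25 | D = 1.81 |
|---|---|---|
| Site test, LVO share 40–60% across sites | 0.07 | 0.07 |
| Site test, LVO share 30–70% across sites | 0.44 | 0.72 |
| Age test, older group 60% of LVO, 50% of non-LVO | 0.14 | 0.24 |
| Age test, older group 60% of LVO, 40% of non-LVO | 0.48 | 0.65 |

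With LVO status in the model, every rate is about 0.05. The same holds for an LVO-only analysis.

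**Level against separation.** Start from AUC 0.90 (D = 1.81).
- Pooled: if both cohort means at one site move 0.5 SD toward each other, D falls to 0.81 and AUC to Φ(0.81/√2) = 0.72. At a 50:50 mix the site mean does not change.
- LVO-only: if only the non-LVO mean at one site moves 0.75 SD toward the LVO mean, D falls to 1.06 and AUC to Φ(1.06/√2) = 0.77. An LVO-only ANOVA contains no data on this.

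**The case against.** The strongest objection is that no model is written down, so the omission of LVO status is inferred. The only sizing tied to the site check counts about 30 LVO subjects per site, and it reproduces as a within-LVO comparison. In such an analysis LVO status can neither enter the error nor confound site or age. This stands, and it is why the pooled figures are conditional. It does not settle the matter: the sizing sentence does not define the ANOVA's analysis set, and the sentence just before the subgroup plan refers to the whole Phase 2 group.

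The effects can also be modest. At an LVO share of 40–60% across sites, the site false-positive rate is barely above nominal. For two sites differing by D = 0.75 with 60 each, power before any post-hoc correction is 0.98 with LVO in the model and still 0.94 or 0.86 without it. Both points stand.

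A reader might infer more than the documents support:
- That LVO status is the largest source of VCI variation. At 28% to 45% it is the largest factor that the documents identify, but variation within cohorts is larger.
- That age differences between sites distort the site comparison. Age group is itself a factor in that model, so they are largely adjusted for; the confounding runs through LVO status.
- That the trial's main result is compromised. The check is a subgroup analysis with no success criterion attached.

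**Conclusion.** The concern holds in conditional form. Section 11.2 leaves the analysis set and the role of LVO status open. On the plain, pooled reading, residual SD rises by a factor of 1.18 to 1.35, and power for one site shifted by 0.5 SD falls from about 0.81 to 0.60 or 0.40. Case mix can then pass for a site or age effect: negligibly for a mild site imbalance, severely (0.44 to 0.72) for an assumed 30–70% spread. On the LVO-only reading this confounding disappears, but shifts in non-LVO subjects go unseen. On both readings, consistency of LVO/non-LVO separation across sites and ages is not tested.

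The figures rest on D = 1.25 as a planning value, on the equal-variance binormal conversion of AUC 0.90, on about 62 scanned subjects per site, and on assumed site and age mixes. The documents do not support saying that a model excluding LVO status has been specified, or that false positives are likely at the mixes that will occur. The primary AUC does not change. The point is worth correcting before the data are analysed.

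**What to change.** Write the model into section 11.2: VCI on LVO status (core-lab read), site and age group, with LVO-by-site and LVO-by-age terms, in all scanned Phase 2 subjects. State the age cut and the post-hoc method. Report AUC by site and by age group with confidence intervals. An analysis within each cohort would also remove the confounding, but would not by itself test separation.

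A random operator effect within site is optional. Section 4.18 already records the user, and a site factor alone cannot tell operators apart from differences in population or setting.

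The cost is SAP wording and a little more analysis; cohort, site and age are already collected. Precision will be limited. At AUC 0.90 with 30 per cohort, the Hanley–McNeil variance is [0.09 + 29(0.818 − 0.81) + 29(0.853 − 0.81)]/900 ≈ 0.0017. The standard error is about 0.042 and the 95% half-width about 0.08. Interaction tests and site-level AUCs should therefore be presented as descriptive, and a non-significant interaction should not be read as proof of consistency.
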